4. SUBJECT SELECTION CRITERIA

4.1. Overview

This clinical study can fulfill its objectives only if appropriate patients are enrolled. The following eligibility criteria are designed to select patients for whom study participation is considered appropriate. All relevant medical and non-medical conditions should be taken into consideration when deciding whether this protocol is suitable for a particular subject. Eligibility criteria may not be waived by the investigator and conformance to the eligibility criteria is subject to review in the case of a Good Clinical Practice (GCP) or a regulatory authority audit. Any questions regarding a subject's eligibility should be discussed with the MAPI medical monitor or the PTC Therapeutics medical monitor prior to enrollment.

4.2. Inclusion Criteria

Subjects must meet all of the following conditions to be eligible for enrollment into the study:

- 1. Evidence of signed and dated informed consent/assent document(s) indicating that the subject (and/or his parent/legal guardian) has been informed of all pertinent aspects of the trial.

 Note: If the study candidate is considered a child under local regulation, a parent or legal guardian must provide written consent prior to initiation of study screening procedures and the study candidate may be required to provide written assent. The rules of the responsible Institutional Review Board/Independent Ethics Committee (IRB/IEC) regarding whether one or both parents must provide consent and the appropriate ages for obtaining consent and assent from the subject should be followed.
- 2. History of exposure to ataluren in a prior PTC study in nmDBMD. Note: Patients are considered eligible only if they received ataluren during their participation in one or more prior PTC-sponsored studies of ataluren in nmDBMD. Note: Subjects who have participated in a prior or ongoing PTC study with ataluren in nmDBMD at a trial site in the US or Canada, but reside outside of the US and Canada, may be eligible for this study (with the approval of the PTC Therapeutics Medical Monitor).
- 3. Male sex.

4. Confirmed screening laboratory values within the central laboratory ranges specified in Table 1 below. Note: Confirmation should be performed for out-of-range values to determine if the abnormality is real or artifactual. Values used to establish eligibility should be the last measurements obtained within the screening period.

Table 1. Required Screening Laboratory Values

Organ System	Parameter	Required Value
	Serum total bilirubin	≤1.5 x ULN
Hepatic	Serum GGT	≤1.5 x ULN
	Hepatitis B core antibody and Hepatitis C antibody	Negative
	Serum creatinine	≤ULN
Renal	Serum BUN	≤ULN
	Urine blood (by dipstick)	≤1+
	Serum sodium (Na+)	<grade 2<="" td=""></grade>
	Serum potassium (K+)	<grade 2<="" td=""></grade>
Serum	Serum bicarbonate (HCO₃⁻)	<grade 2<="" td=""></grade>
Electrolytes	Serum magnesium (Mg ²⁺)	<grade 2<="" td=""></grade>
	Serum calcium (Ca ²⁺)	<grade 2<="" td=""></grade>
	Serum phosphorus	<grade 2<="" td=""></grade>

Abbreviations: BUN = blood urea nitrogen, GGT = gamma glutamyl transferase, ULN = upper limit of normal

- In patients who are sexually active, willingness to abstain from sexual intercourse or employ a barrier or medical method of contraception during ataluren administration and the 6-week follow-up period.
- Willingness and ability to comply with scheduled visits, drug administration plan, study
 procedures, laboratory tests, and study restrictions. Note: Psychological, social, familial, or
 geographical factors that might preclude adequate study participation should be
 considered.

4.3. Exclusion Criteria

Prior to treatment with ataluren, it will be confirmed that the patient meets none of the following conditions:

- Exposure to another investigational drug within 1 month prior to start of study treatment.
- Eligibility for another ataluren clinical trial that is actively enrolling study participants.
- Known hypersensitivity to any of the ingredients or excipients of ataluren (Litesse® UltraTM [refined polydextrose], polyethylene glycol 3350, Lutrol® micro F127 [poloxamer 407], mannitol 25C, crospovidone XL10, hydroxyethyl cellulose, vanilla, Cab-O-Sil® M5P [colloidal silica], magnesium stearate).
- Ongoing use of the following medications:
 - a. Coumarin-based anticoagulants (eg., warfarin), phenytoin, tolbutamide, or paclitaxel.
 - Systemic aminoglycoside therapy
- Ongoing uncontrolled medical/surgical condition, ECG findings, or laboratory abnormality that, in the investigator's opinion, could adversely affect the safety of the patient or make it unlikely that follow-up would be completed.

5. ENROLLMENT PROCEDURES

5.1. Source and Number of Subjects

Up to ~96 patients with nmDBMD each received ataluren treatment in a prior PTC-sponsored clinical trial; these patients are all potential candidates for this study.

It is anticipated that patients will be enrolled from investigator sites in countries including Belgium, France, Germany, Italy, Spain, United Kingdom, Sweden, Israel, and Australia.

5.2. Screening and Study Drug Allocation

The investigator or sub-investigator must inform each prospective subject of the nature of the study, explain the potential risks, and obtain written informed consent/assent from the subject and/or the parent/legal guardian prior to performing any study-related screening procedures.

The subject number used in the prior ataluren DBMD study shall be retained for use in this study. This subject number must be used for subject identification on all study-related documents (case report forms [CRFs], laboratory samples, etc).

Any questions regarding the eligibility of a subject should be discussed with the PTC Therapeutics medical monitor.

The relevant site staff will need to supply the Interactive Web Response (IWR) system with the information required by the system (eg, site number, subject number, subject weight in kilograms) to permit study drug allocation.

6. STUDY DRUG ADMINISTRATION

6.1. Investigational Product

6.1.1. Ataluren (PTC124)

Ataluren will be provided as a vanilla-flavored, white to off-white powder for oral suspension. The drug has been manufactured and formulated under cGMP conditions. The formulation includes matrix and suspending agents, surfactants, and various minor excipients that aid in the manufacturing process. The powder for oral suspension is packaged in aluminum-foil, child-resistant sachets and is supplied in dose strengths containing 125, 250, or 1000 mg of the active drug substance. For administration, the powder in the sachet may be mixed with water, milk (skim, 1% fat, 2% fat, whole milk, or lactose-free milk), fruit juice (except apple juice), fruit punch, or in semi-solid food (yogurt, pudding, or applesauce).

6.1.2. Drug Source

Ataluren will be supplied free of charge to the investigator site by PTC Therapeutics for appropriate distribution to the patients/caregivers. It is intended that ataluren will be provided in sufficient supply for a 12-week study period. However, in the event of pending commercial availability of ataluren, drug may be supplied for a treatment period of less than 12 weeks. Resupply may be obtained via the IWR system.

6.1.3. Study Drug Packaging and Labeling

Sachets will be color-coded to indicate dosage strength (125 mg – yellow, 250 mg – pink, 1000 mg – blue). The labeling will bear the text "CAUTION – New Drug – limited by Federal (USA) law to investigational use."

6.1.4. Study Drug Dispensing

Dosing of ataluren will be based on milligrams of drug per kilogram of subject body weight at Screening/Baseline (Visit 1) and will be adjusted to allow for dosing with the available sachet dose strengths. The sachet dosage strengths and number of sachets to be taken per dose will be provided by the EDC system.

The clinic staff (eg, pharmacist or other qualified person) will be responsible for dispensing study drug according to the EDC system directions.

Because of potential changes in subject body weight over time, weight-based dose adjustment will occur every 6 months. Depending upon the magnitude of change in subject body weight since baseline, the number and type of sachets to be used by the subject may remain the same or may be adjusted.

6.1.5. Return of Study Drug

Subjects should return all unused sachets of ataluren to the investigator site at the end of each visit for inventory. The case report forms will serve as the source document for drug supply to the patients and will document the return of any unused drug for compliance assessments.

6.1.6. Storage and Stability

Sachets containing at luren will be shipped and stored at room temperature (\sim 15 to 30°C). The available stability data from representative sample support the use of the drug product for 48 months when stored at room temperature.

6.1.7. Study Drug Accountability

Study personnel must ensure that all ataluren supplies are temperature-monitored and kept in a secure locked area with access limited to authorized personnel. This study product must not be used outside the context of this protocol. Under no circumstances should the investigator or other site personnel supply study product to other investigators or clinics, or allow the supplies to be used other than as directed by this protocol.

The investigator and/or the responsible site personnel must maintain accurate records of the receipt of all ataluren shipped by PTC Therapeutics or its designee, including, but not limited to, the date received, lot number, amount received, and the disposition of all ataluren. Current reconciliation and dispensing records must also be maintained that include the date and amount of drug dispensed, relevant batch and sachet numbers, and subject's assigned study number.

Depending upon the decision of PTC Therapeutics, unused clinical supplies must be destroyed or must be returned to PTC Therapeutics or its designee after the study is completed.

Accountability must be verified by the site monitor prior to return or destruction. Records documenting the date of study drug destruction or shipping, relevant sachet numbers, and amount destroyed or shipped should be kept in the investigator site study file.

6.1.8. Overdose Precautions

For any subject experiencing an overdose (administration of an ataluren dose >4 times the highest intended total daily dose level for this protocol [>160 mg/kg/day]), observation for any symptomatic side effects should be instituted, and vital signs and biochemical and hematological parameters should be followed closely (consistent with the protocol or more frequently, as needed). Appropriate supportive management to mitigate adverse effects should be initiated. Pending the acquisition of sufficient human experience with the drug, use of gastric lavage or induction of emesis is not specifically recommended nor contraindicated.

The PTC Therapeutics medical monitor should be contacted if an overdose occurs. Under applicable regulations, overdosing may be considered an SAE and should be reported accordingly (see Sections 8.1.1 and 8.1.2).

6.1.9. Inadvertent Exposure and Spill Precautions

Reference can be made to the Ataluren Investigator Brochure for current information on inadvertent exposures and spill precautions.

6.2. Study Drug Treatment

6.2.1. Duration of Therapy

Treatment with ataluren in the context of this protocol is anticipated to occur for 240 weeks. The actual duration of ataluren treatment under this protocol will be subject to the following conditions:

- The patient has the right to withdraw consent and discontinue ataluren at any time.
- If the patient's condition substantially worsens after initiating ataluren treatment, the patient
 will be carefully evaluated by the investigator in consultation with the PTC Therapeutics
 medical monitor. The patient will be withdrawn from treatment if continuing would place
 them at risk.
- Upon consultation with the PTC Therapeutics medical monitor, the investigator may withdraw the patient from ataluren treatment, if, in the investigator's clinical judgment, it is not in the patient's best interest to continue.
- The patient will be withdrawn from treatment if he is unable to tolerate ataluren.
- The patient may be withdrawn from this study if he is eligible to participate in another ataluren - nmDBMD clinical study or program.
- This study may be discontinued by the relevant regulatory authority and/or PTC Therapeutics at any time.
- This study may be stopped upon ataluren marketing authorization within the relevant country.

6.2.2. Schedule of Administration

As noted in Table 2 below, 3 doses should be taken per day – the first dose in the morning (10 mg/kg), the second dose during the middle of the day (mid-day – 10 mg/kg), and the third dose in the evening (20 mg/kg). Ideally, each dose should be taken within ~30 minutes after a meal (eg, ~7:00 AM after breakfast, ~1:00 PM after lunch, and ~7:00 PM after dinner). If possible, intervals for dosing should be ~6 hours (±1 hour) between morning and midday doses, ~6 hours (±1 hour) between midday and evening doses, and ~12 hours (±1 hour) between evening doses and the morning dose on the next day.

table 2. Suggested 2, 2, 2			
Dose Designation	Preceding Meal	Example Dosing Times ^a	
Morning	Breakfast	~7:00 AM - 0700 hours (±1 hour)	
		↑	
		~6 hours	
		↓	
Midday	Lunch	~1:00 PM - 1300 hours (±1 hour)	
		↑	
		~6 hours	
		↓	
Evening	Dinner	~7:00 PM - 1900 hours (±1 hour)	
		↑	
		~12 hours	
		↓	
Next Day Morning	Breakfast	7:00 AM - 0700 hours (±1 hour)	

a Dosing times are examples and may be varied to suit each subject's schedule. However, the time between morning and midday doses and between midday and evening doses should be maintained at ~6-hour intervals, while the time between the evening and next morning dose should be maintained at an ~12-hour interval.

6.2.3. Instructions for Delays in Dosing

If a subject experiences a delay in the administration of ataluren of ≤ 1 hour, the planned dose should be taken with no changes to the subsequent dose schedules. For a subject who has a delay of >1 hour but ≤ 4 hours, the planned dose should be taken; however, all future doses for that day should be shifted later by an approximately corresponding amount. For a subject who has a delay in administration of ataluren of >4 hours, the dose should not be taken. Ataluren administration may continue but the missed dose should not be made up and the planned timing of subsequent ataluren dosing should not be altered.

6.2.4. Study Drug Preparation and Storage

Study drug sachets should be stored and monitored at room temperature away from the reach of children until time of reconstitution. The suspension (powder in the sachet) may be mixed with water, milk (skim, 1% fat, 2% fat, whole milk, or lactose free milk), fruit juice (except apple juice), fruit punch, or in semi-solid food (yogurt, pudding, or applesauce). The number of sachets to be taken for a dose should be separated from the total number of sachets dispensed for the subject. The full contents of each packet should be mixed with at least 30 mL (1 ounce) of

liquid, or 3 tablespoons of semi-solid food. The prepared dose should be mixed well before administration. The amount of the liquid or semi-solid food can be increased based on patient preference.

6.3. Safety Monitoring and Study Drug Dose Interruption/Modification

6.3.1. Laboratory Abnormalities and Adverse Events Requiring Evaluation and Potential Drug Interruption/Modification

Subjects must be monitored closely for adverse events or laboratory abnormalities during the course of the study.

For adverse events or laboratory abnormalities, the investigator will use judgment in determining whether the event or abnormality is clinically significant, whether diagnostic evaluation is warranted, and whether potential interruption of ataluren treatment is appropriate. In general, life-threatening (Grade 4) or severe (Grade 3) adverse events or laboratory abnormalities should be considered clinically significant, although recurrent or persistent moderate events (Grade 2) may also be considered clinically significant in certain circumstances. Reference should be made to the Common Terminology Criteria for Adverse Events (CTCAE), Version 3.0 (see http://ctep.cancer.gov/protocolDevelopment/electronic_applications/docs/ctcaev3.pdf) for grading the severity of adverse events and laboratory abnormalities.

If the patient experiences a dose-limiting adverse event related to ataluren, then drug administration can be interrupted, as necessary, until the adverse event resolves or stabilizes to an acceptable degree. If further evaluation reveals that the adverse event is not related to ataluren, treatment will be continued at the original dose level. Alternatively, until full resolution of the ataluren related adverse event, ataluren may be continued at a reduced dose level of 5 mg/kg in the morning, 5 mg/kg at midday, and 10 mg/kg in the evening. If the patient continues to experience dose-limiting adverse events at this lower dose level, ataluren will be discontinued. If the ataluren adverse event is fully resolved, the ataluren dose may be increased back to 10 mg/kg in the morning, 10 mg/kg at midday, and 20 mg/kg in the evening. The PTC Therapeutics medical monitor will be notified of any SAE or any adverse event that leads to dose reduction, interruption, or treatment discontinuation. In addition, the MAPI Safety Department will be notified any SAEs.

Table 3 below provides information on actions to be taken in the event that abnormalities are noted in specified laboratory parameters. Thresholds are provided for interrupting ataluren immediately, for interrupting ataluren after confirmation of a value beyond the threshold, or for continuing ataluren while evaluating for potential drug-related toxicity. For adverse events or laboratory abnormalities not listed in Table 3 below, the investigator should use his/her judgment in determining whether the event or abnormality is clinically significant, whether diagnostic evaluation is warranted, and whether potential interruption of ataluren therapy is appropriate.

Table 3. Safety Monitoring Parameters and Actions To Be Taken

Organ System and Laboratory Parameter	Stop Study Drug Immediately, Confirm Abnormal Value, and Then Start Work-Up	Stop Study Drug After Confirming ^a Abnormal Value, and Then Start Work-Up	Continue Study Drug, Confirm Abnormal Value, and then Start Work-Up ^a
Hepatic			
Serum total bilirubin	≥Grade 3 (≥3.0 x ULN)	Grade 2 (1.5 – 3.0 x ULN)	
Serum GGT	≥Grade 3 (≥5.0 x ULN)	Grade 2 (>2.5 – 5.0 x ULN)	
Serum ALT			↑ of > 150 U/L with stable or ↓ CK
Adrenal			
Plasma ACTH		>ULN (and plasma cortisol <lln)< td="">>ULN (and cortisol WNL)	</lln)<>	>ULN (and cortisol WNL)
Renal			
Serum cystatin C	>2.00 mg/L	>1.33 – 2.00 mg/L	
Serum creatinine	≥ Grade 2 (≥1.5 x ULN for age)	Grade 1 (>ULN – 1.5 x ULN for age)	
Serum BUN	≥3.0 x ULN	≥1.5 – 3.0 x ULN	
Urine protein: urine creatinine (spot)		>0.40 mg:mg	
Urine protein: urine osmolality (spot)		>0.30 mg/L:mOsm/kg	
Urine blood (by dipstick)	4+ (Large)	3+ (Moderate)	2+ (Small)
Serum electrolytes	Grade 3-4	Grade 2	Grade 1
Serum Na+, high	>155 mmol/L	>150 – 155 mmol/L	
Serum Na+, low	<130 mmol/L		
Serum K+, high	>6.0 mmol/L	>5.5 – 6.0 mmol/L	
Serum K+, low	<3.0 mmol/L		
Serum Mg ²⁺ , high	>1.23 mmol/L		
Serum Mg ²⁺ , low	<0.4 mmol/L	<0.5 – 0.4 mmol/L	
Total serum Ca ²⁺ , high	>3.1 mmol/L	>2.9 – 3.1 mmol/L	
Total serum Ca ²⁺ , low	<1.75 mmol/L	<2.0 – 1.75 mmol/L	
Serum phosphorous	<0.6 mmol/L	<0.8 – 0.6 mmol/L	
Serum HCO ₃ -	<11 mmol/L	<16 – 11 mmol/L	

a Laboratory abnormalities may be confirmed immediately or at the next scheduled clinic visit based on investigator judgment. **Abbreviations:** ACTH = adrenocorticotropic hormone, ALT = alanine aminotransferase, BUN = blood urea nitrogen, Ca²⁺ = calcium, CK = creatine kinase, GGT = gamma glutamyl transferase, HCO₃₋ = bicarbonate, K+ = potassium, Mg²⁺ = magnesium, Na+ = sodium, ULN = upper limit of normal, WNL = within normal limits

It should be noted that blood samples for renin and aldosterone determinations will also be obtained at screening, and, as necessary, for patients with treatment-emergent evidence of adrenal dysfunction. Changes in these laboratory parameters alone will not be exclusionary or reason for study drug discontinuation because renin and aldosterone values are markedly affected by age and normal reference ranges are too narrow to reliably use as guidance for treatment discontinuation in this study population. In addition, renin and aldosterone values may be affected by angiotensin-converting enzyme (ACE) inhibitors, and angiotensin-receptor blockers (ARBs). Changes in renin and aldosterone will be viewed in context with other laboratory findings.

6.3.2. Evaluation of Adverse Events or Laboratory Abnormalities

While specific monitoring, diagnostic testing, and supportive care measures must be instituted based on the clinical judgment of the investigator, investigators are encouraged to contact the PTC Therapeutics medical monitor to obtain guidance and to ascertain whether similar events are being seen at other investigator sites. The PTC Therapeutics medical monitor should be notified of any adverse event or laboratory abnormality that leads to dose interruption and should be apprised of ancillary laboratory or other diagnostic findings and the evolving data from any work-up of the initial abnormality. The PTC Therapeutics medical monitor may suggest review of the case with gastroenterology, endocrinology, or nephrology consultants or with other experts (either at the site or retained by PTC Therapeutics).

Clinical evaluations for potential hepatic, adrenal, and renal toxicities may include the following:

- Hepatic: The medical history, hepatitis screening results, all clinical blood values
 (particularly serum bilirubin, GGT, AST, and ALT values), and all concomitant medications
 should be reviewed. Depending upon changes observed, the recommended diagnostic
 workup may include more frequent monitoring or further evaluations for viral hepatitis and
 immune disorders; tests for cholelithiasis; or abdominal ultrasound, computed tomography
 (CT), magnetic resonance imaging (MRI), or other imaging methods.
- Adrenal: The medical and family history, all clinical blood values (particularly previous
 adrenocorticotropic hormone (ACTH), cortisol, renin, and aldosterone values and serum
 potassium and sodium concentrations), and all concomitant medications (particularly
 corticosteroids, ACE inhibitors, and ARBs) should be reviewed. Depending upon the
 changes observed, recommended diagnostic workup may include further evaluations of
 plasma ACTH, cortisol, and aldosterone levels; serum electrolytes; ACTH stimulation
 testing; reassessment of plasma renin and aldosterone after interruption of ACE inhibitor or
 ARB treatment; CT, MRI, or other imaging methods; and/or adrenal biopsy.
- Renal: The medical history, baseline ultrasound data, all clinical blood and urine renal
 values, serum electrolytes, medications, and potential pre- or post renal conditions should be
 reviewed. Depending upon the changes observed, recommended diagnostic workup may
 include further evaluations of blood or urine; tests of glomerular filtration rate (GFR),
 concentrating ability, or other renal functions; CT, MRI, or other imaging methods; and/or
 renal biopsy.

6.3.3. Instructions for Resuming Study Drug Administration after an Interruption for Safety Concerns

In deciding whether to reinstitute therapy after a dose interruption for any clinically significant safety concern, the investigator should consider factors such as the type and severity of the adverse event or laboratory abnormality, the potential causal relationship of ataluren therapy, the subject's status in terms of DBMD or other health conditions, and the ability to monitor for recurrence of the event.

For hepatic, adrenal, or renal events (refer to Table 3), the level of investigator certainty that an abnormality leading to drug interruption is drug-related should be considered strongly in deciding

whether or not to reinstitute at luren treatment. If the investigator considers the hepatic, adrenal, or renal event to that led to at a luren interruption to be probably related to at a luren, restarting the at a luren is not advised. In this case, the subject should be discontinued from the study (see Sections 6.3.4 and 9). If the investigator considers the hepatic, adrenal, or renal event that prompted at a luren interruption to be possibly related or unlikely related to at a luren, the investigator should use best judgment in determining whether to restart at a luren. If the hepatic, adrenal, or renal event is considered unrelated to at a luren, reinstitution of at a luren is recommended.

If the investigator believes it is appropriate to do so and the PTC Therapeutics medical monitor has been consulted, ataluren may be re-initiated. If the event was determined to be unrelated to ataluren, the study drug may be resumed at full dose. Otherwise, if the drug is resumed, it should be reinitiated at half of the original dose (5-, 5-, 10-mg/kg). The appropriate clinic staff should instruct the subject/caregiver about the revised number of ataluren sachets to be used per dose according to the new schedule.

In general, after dose reduction, the dose should not be returned to the original dose level. However, if further evaluation reveals that the adverse event that led to dose reduction was not related to the ataluren, the dose may be returned to the original dose level. The appropriate clinic staff should instruct the subject/caregiver about the revised number of ataluren sachets to be used per dose according to the schedule provided by the IWR system.

If after dose reduction, the subject experiences a recurrence of a previous abnormality that led to ataluren dose interruption or experiences the new occurrence of an unacceptable adverse event or laboratory abnormality, the investigator should interrupt ataluren and confer with the PTC Therapeutics medical monitor regarding the potential need to discontinue ataluren permanently.

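### Protocol 6.3.1 and 6.3.3 are not reconciled on returning to full dose after a resolved ataluren-related event, or on discontinuing for further events at the reduced dose

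*Protocol*

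**What the plan says.** **Protocol 6.3.1.** For a dose-limiting event related to ataluren, the drug can be interrupted. Alternatively, "until full resolution of the ataluren related adverse event, ataluren may be continued at a reduced dose level of 5 mg/kg in the morning", with 5 mg/kg at midday and 10 mg/kg in the evening. Two consequences follow:

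- On resolution: "If the ataluren adverse event is fully resolved, the ataluren dose may be increased back to 10 mg/kg in the morning", with 10 mg/kg at midday and 20 mg/kg in the evening.
- On further trouble: "If the patient continues to experience dose-limiting adverse events at this lower dose level, ataluren will be discontinued".

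**Protocol 6.3.3.** When drug is restarted after an interruption and the event was not judged unrelated, it restarts at the same half dose. Then:

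- On return to full dose: "In general, after dose reduction, the dose should not be returned to the original dose level". The one exception given is that "if further evaluation reveals that the adverse event that led to dose reduction was not related to the ataluren, the dose may be returned" to its original level.
- On further trouble: "If after dose reduction, the subject experiences a recurrence of a previous abnormality that led to ataluren dose interruption", or has a new unacceptable event or laboratory abnormality, then "the investigator should interrupt ataluren and confer with the PTC Therapeutics medical monitor regarding the potential need to discontinue ataluren permanently".

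The SAP reproduces the laboratory stopping thresholds in its Table 2 but does not address re-escalation or further events at the reduced dose. Its statement that it supersedes the protocol where they conflict therefore settles nothing here.

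**The concern.** An investigator with a dose-reduced patient finds two answers to each of two questions: may the full dose be resumed once a related event has resolved, and must ataluren be stopped if dose-limiting events go on at the lower dose? These are safety instructions in a mainly paediatric population, so the ambiguity matters in itself.

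It also reaches the analysis. The primary objective (Protocol 3.1, SAP 3.1) is long-term safety and tolerability at 10, 10, 20 mg/kg.

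- **Re-escalation** determines the dose at which later adverse events accrue. The exposure-adjusted incidence in SAP 5.7.1 counts days on study drug without regard to dose, so a day at the reduced dose and a day at the full dose weigh the same.
- **Further events at the reduced dose** can determine whether the patient is counted among adverse events leading to discontinuation (Protocol 10.4.5.1, SAP 5.7.1), and whether he is an event in the Kaplan-Meier analysis of time to discontinuation (SAP 5.2).

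Protocol 10.4.3 calls for a description of dose modifications for each patient, but SAP 5.6 specifies only compliance and treatment duration. Apart from the by-patient listings, the planned output would not show which rule had been followed.

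**Working it through.** There is no statistical figure to reproduce: Protocol 10.1 states that the sample size rests on no formal hypothesis. The check is a comparison of the two sections, plus the daily doses.

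**Daily dose**

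- Full dose: 10 + 10 + 20 = 40 mg/kg/day.
- Reduced dose, the same in both sections: 5 + 5 + 10 = 20 mg/kg/day.
- Ratio: 40 / 20 = 2.

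**The situations, taken one at a time**

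| Situation | Protocol 6.3.1 | Protocol 6.3.3 | Agree? |
|---|---|---|---|
| Event found unrelated to ataluren | Original dose | Original dose allowed | Yes |
| Related event, not fully resolved | Permission to re-escalate does not arise | In general no return to original dose | Yes |
| Related event, fully resolved | Return to 40 mg/kg/day permitted | In general stay at 20 mg/kg/day; resolution is not an exception | **No** |
| Dose-limiting events continue or recur at the reduced dose | Discontinuation mandatory | Interrupt, then confer; discontinuation is a possibility | **No** |
| New unacceptable event or laboratory abnormality at the reduced dose that is not clearly dose-limiting | Not clearly covered | Interrupt, then confer | No clear conflict |
| Hepatic, adrenal or renal event that led to interruption, judged probably related | No separate rule | Restart not advised; patient leaves the study | Reduced dose not reached by this route |

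Two rows conflict. In the third row the conditions differ in kind: 6.3.1 turns on *resolution* of a related event, while 6.3.3 turns on *absence of relationship*. A related, resolved event meets the first and fails the second. In the fourth row one section uses an obligation and the other leaves the outcome to a case-by-case decision.

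**Does any other text settle it?**

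- *Section headings.* 6.3.3 is headed as applying after an interruption, and 6.3.1 offers the reduced dose as an alternative to interrupting. But the 6.3.3 sentence on not returning to the original dose applies after dose reduction without limit, and 6.3.1 covers interruption too.
- *Protocol 13.2.4.* It asks that the recommendations be applied flexibly, but it concerns interruption by severity grade. It does not say which section governs re-escalation or further events.
- *Cross-references.* Neither section points to the other on these two questions.

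**The case against.** The best case for the protocol is that the two sections can be obeyed together. Section 6.3.1 gives a permission to re-escalate and 6.3.3 gives qualified general advice against it, so a site that never re-escalates after a related event breaches neither. Likewise, a site that interrupts, confers and then always discontinues satisfies both. The medical monitor is notified of adverse events leading to reduction, interruption or discontinuation (6.3.1), consulted before restart and on recurrence (6.3.3), and consulted before permanent discontinuation for safety (6.3.4). That should reduce variation between sites.

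Much of this stands, and it rules out three stronger readings that a reader might draw:

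- *That the rules are opposite and sites cannot follow both.* This is true only for a site that uses the 6.3.1 permission to re-escalate, or the 6.3.3 discretion to continue after further dose-limiting events.
- *That every dose-reduced patient is affected.* The table above shows otherwise: unrelated events and unresolved related events raise no re-escalation conflict, and the triggers for further events overlap only in part.
- *That dose-modification and discontinuation counts are not comparable.* The study is uncontrolled, its summaries are descriptive and pooled, and no comparison between sites is planned. Variation by site is possible but not demonstrated. Dose-modification counts are also not part of the primary endpoint as defined in Protocol 3.3.

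What does not stand is the conclusion that no correction is needed. Nothing instructs sites to take the stricter reading, and a medical monitor applying the protocol has the same two texts to work from.

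**Conclusion.** The inconsistency is real on two points, and the protocol is wrong as written in the sense of an internal contradiction. After a fully resolved related event, the two sections lead to daily doses that differ by a factor of 2, which is simply the protocol's own reduction step. After further dose-limiting events at the reduced dose, one section requires discontinuation and the other leaves it open.

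The patients affected are dose-reduced patients whose related event fully resolves, and those who have further dose-limiting events at the reduced dose. The documents give no expected number. Protocol 2.2.3.2.1 and 2.2.3.2.2 report that no patient discontinued because of an adverse event in Studies 004 and 007, so the number may be small. Those sections give no counts of dose reductions, however, so the frequency remains unknown.

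The conclusion rests only on the wording of the two sections in the protocol text supplied, which runs to Week 240. SAP 1 mentions a later version for Canadian sites extended to Week 336; whether the same wording persists there could not be checked. No view is taken on which rule is clinically right.

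**What to change.** 1. **Protocol.** Reconcile 6.3.1 and 6.3.3 into one rule on return to the original dose after reduction and one rule on further events at the reduced dose. Each should have a single stated trigger, and each section should cross-refer to the other. Which rule to adopt is the sponsor's clinical decision.
2. **Study report.** SAP 5.2 records that the sponsor has decided to discontinue the study, which limits what an amendment can still change. The report should therefore state, for each dose-reduced patient, which rule was applied: whether the dose was returned to the original level after a related event, and whether further events at the reduced dose led to discontinuation or to interruption with resumption.

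The cost is a wording clarification or amendment, plus one short listing. Protocol 10.4.3 already calls for dose modifications and the reasons for deviating from planned therapy to be described for each patient, and by-patient listings of each CRF module are already planned, so little or no new data collection should be needed.
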